6.2 Analysis of secondary endpoints

- 1. Immunogenicity: The median and range of values of ELISPOT response will be plotted by group at baseline and follow-up.
- 2. Immune and clinical responses to Vaccination: medians and IQR or numbers and proportions (as appropriate), will be presented at baseline and follow up for the following outcomes:
 - Crohn's disease activity
 - Quantity of MAP in blood

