3.1 SYNOPSIS

Trial Title Trial Centres	A clinical trial to determine the safety, tolerability and immunogenicity of the candidate Mycobacterium avium subspecies paratuberculosis (MAP) vaccine ChAdOx2 HAV and MVA HAV in patients with active Crohn's disease Guy's and St Thomas' NHS Foundation Trust, [name]
Trial Identifier	HAV002
Clinical phase	Ib
Design	Open label, dose escalation, heterologous prime-boost study
Population	Patients with active Crohn's disease aged 18 – 50
Planned Sample Size	Participants receiving ChAdOx2 HAV will be recruited and vaccinated 6 per group, with the usual lead in for each group, up to a maximum of 12 Participants receiving MVA HAV only (n=6) will be recruited into 2 groups. A total of 10 participants will be recruited into a prime-boost group with ChAdOx2 HAV-MVA HAV Maximum possible sample size for study (n=28)
Follow-up duration	20 weeks for participants receiving ChAdOx2 HAV only 12 weeks for participants receiving MVA HAV only 20 weeks for participants receiving ChAdOx2 HAV and MVA HAV
Primary Objectives	To assess the safety and tolerability of ChAdOx2 HAV and MVA HAV in patients with active Crohn's disease administered alone and in a prime-boost regimen
Secondary Objectives	To assess the immunogenicity of ChAdOx2 HAV and MVA HAV in patients with active Crohn's disease administered alone and in a prime-boost regimen
Investigational	ChAdOx2 HAV - Viral vectored vaccine using a chimpanzee
Product	adenovirus as a vector encoding a Mycobacterium avium subspecies paratuberculosis (MAP) insert designated HAV
	MVA HAV - Viral vectored vaccine using a modified vaccinia

	Ankara as a vector encoding a Mycobacterium avium subspecies paratuberculosis (MAP) insert designated HAV
Finished products and doses	1. ChAdOx2 HAV at 2.5 x 10 ¹⁰ vp
r misrica products and doses	2. ChAdOx2 HAV at 5 x 10 ¹⁰ vp
	3. MVA HAV at 5 x 10 ⁷ pfu
	4. MVA HAV at 2 x 10 ⁸ pfu
Form	Liquid
Route	Intramuscularly (IM) into the deltoid region of the arm

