3.3 Secondary objective

To assess the immunogenicity and clinical response of ChAdOx2 HAV and MVA HAV in patients with active Crohn's disease on no immunosuppressive therapy when administered alone and in a prime-boost regimen.

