6.3 Statistical considerations

Time points

The primary outcome is measured across all follow-up time period (2 or more participants experiencing Grade 3 severe adverse reactions (SAR) lasting more than 48 hrs). Secondary outcomes are presented using descriptive statistics for baseline and follow-up timepoints. Data will be presented using descriptive statistics and no repeated measures analysis will be conducted.

Stratification and clustering

There will be no stratification or clustering

Missing baseline data

Individuals must have all baseline measurements as part of screening and as standard of care. This data will not be imputed for the primary analysis.

Missing outcome data

Individuals will be monitored for the entire followup duration and thus there will be no missing data for the primary outcome. If data is missing for the secondary or exploratory outcomes analysis will be carried out on a complete case basis with no imputation.

Method for handling multiple comparisons

Bonferroni adjustment for multiple comparisons will be used.

Method for handling non-compliance (per protocol/CACE analyses)
Since this is a single arm trial CACE analysis is not possible

Model assumption checks

Only descriptive statistics will be presented for all outcomes and thus no model assumption checks are needed. As the sample size is small, medians and IQRs will be presented instead of means and standard deviations.

Sensitivity analyses

No sensitivity analyses are planned

Planned subgroup analyses

No subgroup analyses are planned

Interim analysis

Interim safety reviews are planned after vaccinating the first participants in all groups, and prior to moving up a dose. The safety reviews are summarized in the table below, and described in more detail in section 4.4 to 4.7

Safety reviews

Table 7 Planned interim safety reviews

Interim safety	When
review	
1	After vaccination of the first participant in
	Group 1
2	After vaccination of the participant 2 and 3
	in Group 1, and prior to vaccinating
	participants 4-6 in Group 1 and participant
	1 in Group 2
3	After vaccination of the first participant in
	Group 2
4	After vaccination of the first participant in
	Group 3
5	After vaccination of the participant 2 and 3
	in Group 3, and prior to vaccinating the first
	participant in Group 4
6	After vaccination of the participant 2 and 3
	in Group 4, and prior to vaccinating the first

	participant in Group 5
--	------------------------

7 Software

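### Section 6.2 summarises ELISPOT and Crohn's disease activity only by group at each time point, so the planned output cannot show how many participants rose or fell, or by how much

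*SAP*

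**What the plan says.** The secondary objective (SAP 3.3) begins: "To assess the immunogenicity and clinical response of ChAdOx2 HAV and MVA HAV in patients with active Crohn's disease". Section 6.2 sets the analysis. For ELISPOT: "The median and range of values of ELISPOT response will be plotted by group at baseline and follow-up". For Crohn's disease activity: "medians and IQR or numbers and proportions (as appropriate), will be presented at baseline and follow up for the following outcomes". Section 6.3 adds: "Data will be presented using descriptive statistics and no repeated measures analysis will be conducted". On missing values, 6.3 says: "If data is missing for the secondary or exploratory outcomes analysis will be carried out on a complete case basis with no imputation". It does not say whether a complete case has values at all time points or only at the one being summarised.

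The data are repeated measurements on the same people:

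- **ELISPOT.** Section 3.3.1 and the schedules give immunology blood on days 0, 28 and 56 in Groups 1 and 2, and on days 0, 28, 56, 84 and 112 in Group 5 (plus a screening sample). The immunology row for Groups 3 and 4 is blank, and 3.3.1 lists no sample for them.
- **Crohn's disease activity.** It is assessed at screening and day 56 in all groups, and also on day 112 in Group 5.

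No change score, fold change, responder count or individual profile is planned for either outcome.

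**The concern.** With no control arm, a response to vaccination can only be read as a change within a person from before to after. A median at baseline beside a median at follow-up does not give that. The difference between two medians is in general not the median of the differences, and neither median says who moved in which direction. In groups this small, a reader will want to know whether a higher follow-up median reflects a rise in nearly everyone or a large rise in a few.

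The undefined complete-case set adds a second problem. If each time point uses whoever has a value, the baseline and follow-up medians may describe different people, and a shift can appear although nobody changed.

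In Group 5, 6.2 refers only to baseline and follow-up. It plans no comparison with day 56, the day of the boost, although the prime-boost regimen is part of the objective.

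**Working it through.** **Inputs from the SAP.** Group sizes are 6, 6, 3, 3 and 10 (3.1 and Table 1). Their sum is 6 + 6 + 3 + 3 + 10 = 28, which matches the stated maximum. The SAP gives no precision figure for these outcomes, so there is none to reproduce. Sizes for ELISPOT are 6, 6 and 10 (22 of 28 participants); sizes for Crohn's activity are 6, 6, 3, 3 and 10.

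**Assumptions.** The SAP gives neither the within-person correlation r nor the amount of missing data. The values below are illustrative.

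**1. Same planned summary, different responses (n = 6).** Baseline values are 10, 20, 40, 80, 160, 320: median (40 + 80)/2 = 60.

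| | Follow-up, in the same order of persons | Median | Range | Rise / same / fall |
|---|---|---|---|---|
| A | 20, 40, 80, 160, 320, 640 | 120 | 20 to 640 | 6 / 0 / 0 |
| B | 640, 320, 160, 80, 40, 20 | 120 | 20 to 640 | 3 / 1 / 2 |

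The follow-up values are the same six numbers, so any summary of that time point alone, the IQR included, is identical.

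Within-person changes are 10, 20, 40, 80, 160, 320 in A and 630, 300, 120, 0, −120, −300 in B. The median change is 60 in both: (40 + 80)/2 and (120 + 0)/2. The median fold change is 2.0 in A and (4 + 1)/2 = 2.5 in B. So the median change alone would not separate A from B either. The range does (10 to 320 against −300 to 630), and so do the individual lines. A fix that added only the median change would be incomplete.

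**2. Missing values.** Suppose nobody changes and the two highest participants are missing at follow-up.

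- Each time point summarised on whoever is present: baseline median 60, follow-up median (20 + 40)/2 = 30. The median halves with every observed change equal to zero.
- The same four participants at both times: 30 and 30. The artefact is gone.

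With one missing, the follow-up median is 80 if one of the three lowest is absent and 40 if one of the three highest is absent, again against a baseline of 60.

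**3. Precision.** For means, a paired change has variance 2s²(1 − r)/n, and a difference between two independent samples has 2s²/n; the ratio is 1 − r. That comparison does not apply here. Both time points come from the same people, and with complete data the difference of the two means is the mean change, so the ratio is 1. For the medians that the SAP uses, simulation from a bivariate normal with equal variances and complete data gives the following for variance(median change) / variance(difference of medians):

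| r | n = 3, 6, 10 | 1 − r |
|---|---|---|
| 0.5 | 0.80 to 0.84 | 0.50 |
| 0.7 | 0.68 to 0.74 | 0.30 |
| 0.8 | 0.67, 0.67, 0.60 | 0.20 |

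The last row comes from simulated standard deviations, in units of the between-person SD: (0.423/0.516)² = 0.67, (0.293/0.357)² = 0.67, (0.235/0.304)² = 0.60.

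**The case against.** The best defence is that 6.3 deliberately limits a small phase Ib trial to descriptive statistics, that no test, interval or dose decision depends on these outcomes, and that 6.2 does not forbid individual plots. Section 5.5 also reports missingness for each variable at each time point and compares the baseline characteristics of those with and without follow-up, so a shift caused by absent participants might be noticed. All of this stands, and it limits the importance of the point. It does not remove it: a median and range of changes and a line plot are also descriptive and need no repeated measures model. The SAP itself lists change from baseline as an outcome for safety laboratory measures (3.2.2).

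Four stronger readings are tempting, and the document does not support them:

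- **That ignoring the pairing costs 50% to 70% of the variance.** This takes 1 − r from the wrong comparison; step 3 of the working gives the figures for medians.
- **That ELISPOT is summarised in groups of three.** No immunology sample is scheduled in Groups 3 and 4. Groups of three apply to Crohn's activity only.
- **That the plan necessarily mixes response with who is missing.** The text says only "analysis will be carried out on a complete case basis with no imputation". If that means the same participants at both times, the problem does not arise.
- **That change from day 56 in Group 5 would isolate the effect of the boost.** Immunology sampling in Groups 1 and 2 ends at day 56, so there is no prime-only comparison afterwards. Section 6.3 also speaks of follow-up time points in the plural, so values before and after the boost may well be shown; what is not planned is the change within a person.

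**Conclusion.** The point holds as a low-cost improvement to two secondary outcomes. The planned summaries cannot show how many participants rose or fell, or by how much. That follows from 6.2 alone and needs no assumption about correlation or missing data; the six-person example only illustrates it. The concern about different people at the two times is conditional on how the complete-case rule is applied, which 6.3 leaves open. The gain in precision is modest and rests on assumed normality, equal variances, complete data and r of 0.5 to 0.8: a variance ratio of about 0.8 at 0.5 and about 0.7 at 0.7. The main reason for the change is that the output would then describe individual response. The primary safety analysis is unaffected.

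**What to change.** In 6.2:

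1. For each scheduled post-baseline time point, add the median and range of within-participant change from baseline, by group, among participants with both values, and state the paired n. For ELISPOT use fold change with a stated rule for zero baseline counts, or absolute change.
2. Plot individual lines by group for both outcomes. These show the direction and size of each participant's change, which the median change alone can miss.
3. For Group 5, also report change from day 56 to days 84 and 112 for ELISPOT, and from day 56 to day 112 for Crohn's activity (not assessed on day 84). Label it post-boost change, not an isolated boost effect.

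In 6.3, define the complete-case set for these summaries.

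The cost is a few sentences, some extra table columns and a line plot per outcome. All data are already scheduled for collection, and no model, test or additional visit is needed.

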6.3 Statistical considerations

Time points

The primary outcome is measured across all follow-up time period (2 or more participants experiencing Grade 3 severe adverse reactions (SAR) lasting more than 48 hrs). Secondary outcomes are presented using descriptive statistics for baseline and follow-up timepoints. Data will be presented using descriptive statistics and no repeated measures analysis will be conducted.

Stratification and clustering

There will be no stratification or clustering

Missing baseline data

Individuals must have all baseline measurements as part of screening and as standard of care. This data will not be imputed for the primary analysis.

Missing outcome data

Individuals will be monitored for the entire followup duration and thus there will be no missing data for the primary outcome. If data is missing for the secondary or exploratory outcomes analysis will be carried out on a complete case basis with no imputation.

Method for handling multiple comparisons

Bonferroni adjustment for multiple comparisons will be used.

Method for handling non-compliance (per protocol/CACE analyses)
Since this is a single arm trial CACE analysis is not possible

Model assumption checks

Only descriptive statistics will be presented for all outcomes and thus no model assumption checks are needed. As the sample size is small, medians and IQRs will be presented instead of means and standard deviations.

Sensitivity analyses

No sensitivity analyses are planned

Planned subgroup analyses

No subgroup analyses are planned

Interim analysis

Interim safety reviews are planned after vaccinating the first participants in all groups, and prior to moving up a dose. The safety reviews are summarized in the table below, and described in more detail in section 4.4 to 4.7

Safety reviews

Table 7 Planned interim safety reviews

Interim safety	When
review	
1	After vaccination of the first participant in
	Group 1
2	After vaccination of the participant 2 and 3
	in Group 1, and prior to vaccinating
	participants 4-6 in Group 1 and participant
	1 in Group 2
3	After vaccination of the first participant in
	Group 2
4	After vaccination of the first participant in
	Group 3
5	After vaccination of the participant 2 and 3
	in Group 3, and prior to vaccinating the first
	participant in Group 4
6	After vaccination of the participant 2 and 3
	in Group 4, and prior to vaccinating the first

	participant in Group 5
--	------------------------

7 Software

Data management: The KHP-CTO will provide a fully validated and computer system compliant database for the trial data. Data management including: raising data queries, data extractions for analysis (interim and final) and database locks will be conducted by the KHP-CTO on behalf of the sponsor. The CTO Data Manager will extract data periodically as needed and provide these in comma separated (.csv) format.

Statistical analysis: R (R Core Team (2020). R: A language and environment for statistical computing. R Foundation for Statistical Computing, Vienna, Austria. URL https://www.R-project.org/.) will be used for data description and the main inferential analysis.

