3.3.1 Secondary outcome measures

Immunogenicity

Measures of immunogenicity may include:

ELISPOT to enumerate IFN-γ producing T cells

Other exploratory immunology may be carried out in collaboration with other specialist laboratories. This would involve transfer of serum/plasma and/or peripheral blood mononuclear cells (PBMC), but samples would be anonymised. Participants will be consented for this.

Sampling of exploratory immunology responses

20ml of whole blood will be taken at baseline (D0) and days 28 and 56 (groups 1 and 2). For Group 5 10ml of whole blood will be taken at screening, with 30ml taken at baseline (D0) and days 56 and 112 and an additional 20ml on days 28 and 84 of the study for use in assays to measure immune responses of various types to the vaccine.

Assessment of clinical response

All participants will undergo an evaluation of Crohn's disease activity at screening and at day 56 for groups 1-4. Group 5 will undergo an evaluation of Crohn's disease activity at screening, on day 56 and again on day 112. For Group 5, endoscopic scoring by flexible sigmoidoscopy or colonoscopy will be undertaken by the CD-SES (simple endoscopic score) at screening and at day 112.

Exploratory immunology may be carried out in collaboration with other specialist laboratories. This would involve transfer of serum/plasma and/or peripheral blood mononuclear cells (PBMC), but samples would be anonymised. Participants will be consented for this.

4 Trial design

This is a phase Ib open-label dose escalation study to assess the safety, tolerability and immunogenicity of the candidate Mycobacterium avium subspecies

paratuberculosis (MAP) vaccine, ChAdOx2 HAV in patients with active Crohn's disease aged 18-50.

Participants will be enrolled and doses will be escalated according to a study plan which will run as outlined in section 8.4.2.2 of the protocol and summarized in the table below:

Table 1 Summary of dosing regimen

Group	Dose
1 (n=6)	ChAdOx2 HAV, 2.5x1010 vp
2 (n=6)	ChAdOx2 HAV, 5x1010 vp
3 (n=3)	MVA HAV, 5x107 pfu
4 (n=3)	MVA HAV, 2x10 ₈ pfu
5 (n=10)	Prime boost Regime (doses depended on
	the results from Groups 1-4)

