5.5 Loss to follow-up and other missing data

The proportions of participants missing each variable will be summarised at each time point.

The baseline characteristics of those missing follow up will be compared to those with complete follow up.

The reasons for withdrawal from the trial will be summarised.

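### Crohn's disease activity is summarised on complete cases with no sensitivity analysis, which biases clinical response towards improvement if participants withdraw because their disease worsens

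*SAP*

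**What the plan says.** The secondary objective (SAP section 3.3) is "To assess the immunogenicity and clinical response of ChAdOx2 HAV and MVA HAV in patients with active Crohn's disease on no immunosuppressive therapy", given alone or as prime-boost. Section 3.3.1 sets the assessment times: "All participants will undergo an evaluation of Crohn's disease activity at screening and at day 56 for groups 1-4". Group 5 is assessed at screening, day 56 and day 112, with an endoscopic score at screening and day 112.

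Section 6.2 lists Crohn's disease activity as a secondary endpoint, for which "medians and IQR or numbers and proportions (as appropriate), will be presented at baseline and follow up". For missing values, section 6.3 says: "If data is missing for the secondary or exploratory outcomes analysis will be carried out on a complete case basis with no imputation". The same section adds: "No sensitivity analyses are planned". It also requires all baseline measurements to be present and describes the trial as single arm.

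Section 5.5 asks for the proportion missing each variable at each time point and a baseline comparison of those with and without follow-up. It adds: "The reasons for withdrawal from the trial will be summarised". Table 5 in section 5.2 lists each participant's withdrawal date and reason.

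**The concern.** In Groups 1-4 the only activity assessment after vaccination is at day 56, so anyone who leaves before then contributes no follow-up value. Worsening disease is a foreseeable reason to leave a trial of active Crohn's disease entered without immunosuppressive therapy. In that case the missing value depends on the outcome itself. The baseline summary covers everyone and the follow-up summary covers those who stayed. The comparison then describes activity among those who remained, while the objective concerns those who were vaccinated.

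With no control arm, this before-after comparison is the only clinical-response evidence in the plan. Groups of 3 to 10 are small enough for one leaver to move the median.

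**Working it through.** **Inputs from the SAP.** Group sizes are 6, 6, 3, 3 and 10, and 6 + 6 + 3 + 3 + 10 = 28, which reproduces the stated maximum. The SAP gives no withdrawal rate, standard deviation or expected effect for Crohn's activity. What follows therefore rests on assumptions.

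**Step 1: bias in the median change.** Assume changes are normal with mean 0 (no true change), higher values mean worse disease, and the k participants with the worst change leave. The complete-case median is then a lower order statistic of the full group. Its expected value, in SDs of individual change, is:

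| Group size | Leavers | Median of those left | Expected value |
|---|---|---|---|
| 10 | 1 | 5th of 10 | -0.12 |
| 10 | 2 | mean of 4th and 5th of 10 | -0.25 |
| 6 | 1 | 3rd of 6 | -0.20 |
| 6 | 2 | mean of 2nd and 3rd of 6 | -0.42 |
| 3 | 1 | mean of 1st and 2nd of 3: (-0.846 + 0)/2 | -0.42 |

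The full-group median has expectation 0, so each value is pure bias. Simulation gives the same figures.

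**Step 2: the quantity section 6.2 plans.** The SAP reports medians at each time and does not mention median change. For illustration, take baseline CDAI as uniform on 150-320. That range is one of three alternative activity criteria in section 4.2. Take individual change as normal with mean 0 and an assumed SD of 50 to 100 points. The mean spurious fall (follow-up median of stayers minus baseline median of all) is:

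| Group size | 1 leaver | 2 leavers |
|---|---|---|
| 10 | 8-14 | 15-27 |
| 6 | 12-22 | 23-44 |
| 3 | 21-43 | not used |

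Restricting baseline to the stayers does not help. At n=10, two leavers and SD 70, the shift is -20 points either way.

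**Step 3: when the bias vanishes or is outweighed** (n=10, SD 70).
- Withdrawal unrelated to worsening, two leavers: shift -0.2 points.
- True mean worsening of 20 points: the complete-case change is about +10, 0 and -10 for one, two and three leavers.
- True mean worsening of 40 points: about +30, +20 and +10.

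An apparent improvement is therefore not assured.

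**Step 4: how often a group loses someone.** The chance of at least one leaver is 1 - (1 - p)^n. At an assumed p = 0.10 it is 1 - 0.9^3 = 27%, 1 - 0.9^6 = 47% and 1 - 0.9^10 = 65%. These count withdrawals for any reason.

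**Step 5: proportions.** With 3 responders and 2 leavers, a group of 6 gives 3/4 = 75% on complete cases and 3/6 = 50% of those vaccinated. A group of 10 gives 3/8 = 37.5% and 3/10 = 30%.

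**Step 6: effect of the added summary** (n=10, SD 70, no true change). Ranking the leavers worst changes the mean shift from -10, -20 and -30 points to +1, +4 and +10 for one, two and three leavers. The small positive remainder arises because the person with the largest worsening need not have the highest score at follow-up.

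**The case against.** The strongest reply is that nothing in the SAP says a participant who flares will leave. Section 3.2.3 keeps vaccinated participants under safety follow-up if they consent, and section 6.3 expects monitoring throughout. Someone who flares but attends day 56 or day 112 is assessed and counted. This stands: the bias is conditional.

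Second, sections 5.2 and 5.5 make each leaver and reason visible, and with at most 28 participants a careful reader could see what happened. This also stands as to transparency. But the reported median and proportion stay as they are, and leavers can match stayers at baseline and worsen afterwards.

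Third, the outcome is descriptive. No test or dose decision rests on it, and an uncontrolled shift cannot establish a vaccine effect under any missing-data rule. The one-leaver biases are also smaller than the sampling error of a median: 0.37 SD (n=10), 0.46 SD (n=6) and 0.67 SD (n=3). This limits the consequence. Unlike sampling error, though, the bias has a known direction when withdrawal follows worsening.

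Fourth, worst-ranking has a bias of its own. If a withdrawal unrelated to the outcome is wrongly attributed to worsening, ranking one leaver worst shifts the median change by +0.14 SD (n=10), +0.25 SD (n=6) or +0.56 SD (n=3). This stands, and is why worst-ranking belongs beside the complete-case summary and not in its place.

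**Conclusion.** The point holds as a conditional one. The complete-case rule, with no sensitivity analysis behind it, leaves clinical response open to a favourable bias if withdrawal follows worsening disease. With no true change and the worst participant lost, the bias in the median change is about 0.12 SD (1 of 10), 0.20 SD (1 of 6) or 0.42 SD (1 of 3). If withdrawal is unrelated to worsening it is about zero. The figures assume normal changes. The CDAI-point figures also assume a baseline distribution and SD that the SAP does not give.

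A reader might infer two stronger claims, and the SAP supports neither:
- **That the reported median will show an improvement the vaccine did not cause.** This depends on how many leave, why, and the underlying trend. The SAP gives none of these, and with true worsening the summary can still show worsening.
- **That participants' disease is untreated.** Sections 4.2 and 4.3 exclude immunosuppressive, systemic corticosteroid and biological therapy, not all treatment.

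**What to change.** In section 6.3, keep the complete-case summary. For Crohn's disease activity and the Group 5 endoscopic score, add beside it a summary over all vaccinated participants:
- In the median and IQR, rank as worst anyone whose value is missing after withdrawal for worsening Crohn's disease.
- In any proportion, count that person as not improved.
- State the number contributing at each time point.

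Keep complete-case analysis for ELISPOT.

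The cost is SAP wording and one extra summary column, since withdrawal reasons are already collected. The added figures will be somewhat less favourable and can be biased the other way if a withdrawal reason is misattributed. In groups of 3 an IQR limit may have no numeric value, and nor may the median if two leave. The table should then show such an entry as worst rank.
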